6.6.2 Missing Data

An essential component of the thorough analysis includes an assessment of the impact of missing data on study conclusions. As a part of assessing this impact, supportive analysis will include:

- observed cases by assessment time.

To ensure robustness of analysis conclusions against missingness, multiple imputation methods will also be done to cope with missing data as a key supportive analysis using the final on-treatment assessment of treatment failures as non-missing data at endpoint. Multiple imputations (MI) will be used as a supportive analysis with 100 invocations (acknowledging that more invocations are needed with more missing data). Monte Carlo methods are planned.

In accordance with the recommendations of the report from the National Academy of Science (NAS) panel “*The Prevention and Treatment of Missing Data in Clinical Trials*,” (National Research Council, 2010), missingness is classified as “missing at random” (MAR) or “missing not at random” (MNAR). When subjects are withdrawn due to treatment failure, this event is considered in this sensitivity analysis to be MNAR, and the endpoint value is taken as the hard endpoint (imputed for progression over time) in analysis. Data that are missing for other reasons are considered to be MAR, and standard multiple imputation methods are planned.

6.7 Statistical Methodology for Secondary Analysis

Secondary and exploratory endpoints that are measurement variables will use similar statistical methodology to the methodology used for primary analysis and will also use similar figures as those described in the associated TOC. Efficacy variables that are proportions will be analyzed using Mantel-Haenszel test. For the analysis of the categories for responders, a Cochran-Mantel-Haenszel test will be used.

Secondary endpoints will be performed using LZCF as described above. Composite and GST scores will only be run as LZCF.

Methodologies for variables that are categorical and summarized with proportions will include construction of confidence intervals for each treatment group and for the difference between groups. For analysis, Fisher’s exact test will be used for single-population analysis, and a Mantel-Haenszel test will be used for analyses combining data across strata.

Methodologies for time-to-event variables will include construction of 95% confidence intervals for each group separately and for the difference between groups. For analysis, a Wilcoxon test will be used for single-population analysis.

A graphical representation will be defined where the y-axis will show the cumulative percentage of subjects who achieved the specific measure of improvement or worsening in the ADAS-cog14 total score shown on the x-axis with a separate cumulative percentage curve for each treatment group.

6.8 Disposition, Demography, and Baseline Characteristics

A tabulation of subject disposition will be presented, including the number screened, the number randomized in each population group, the number dosed in each population group, the number who withdrew prior to completing the study, and reasons for withdrawal.

Demographic and baseline characteristics (disease history, medical history, and prior treatments for AD) will be summarized for all randomized subjects and for the FAS. No formal statistical comparisons will be performed. Summaries of continuous variables will include number of subjects, mean, median, minimum, maximum, and standard deviation. Summaries of categorical variables will include numbers of subjects in each category.

The variables to be summarized will include:

- Age, gender, race, and ethnicity
- Weight, height, BMI
- Years since diagnosis of AD
- Education level
- Previous medication for AD (AChEI, Memantine)
- Hypertension Y/N
- Diabetic medication type (ATC4 classification)
- Acetylcholinesterase inhibitor usage (Y/N)
- Memantine usage (Y/N)
- Acetylcholinesterase inhibitor usage (Y/N) and Memantine usage (Y/N)

Summaries will be provided overall and stratified by treatment group.

Additionally, baseline characteristics will be compared for efficacy measures of MMSE, ADAS-Cog14, CDR-sb, FAQ, Amsterdam IADL, HbA1c. No formal statistical comparisons will be performed.

6.9 Analysis of Safety Data

6.9.1 Adverse Events

Adverse events reported in this study will be coded using MedDRA®, Version 16.0, or later. Coding will be to the lowest level terms (LLT). The verbatim text, the preferred term, and the primary SOC will be listed in subject listings. Summaries that include frequencies and proportions of subjects reporting AEs will include the preferred terms and the SOCs. Summaries will include TEAEs by severity and by relationship to study medication.

Adverse event summaries will be constructed displaying AEs in decreasing order of total frequency according to the numbers of subjects reporting the AE (not the number of reports).

- Number (percent) of subjects reporting TEAE by treatment and overall in accordance with variables listed in Section 4.1.1.

Supportive listings will be constructed that includes the subject identification, the treatment group, TEAEs, MedDRA terms, seriousness, severity, causality, elapsed time to onset, duration, and outcome.

Methodology for AESIs will follow the same methodology for TEAEs.

6.9.2 Vital Signs

Subjects with vital signs meeting the criteria in Section 10 of this SAP for values of potential clinical concern will be identified and summarized. Proportions of subjects with vital signs of potential clinical concern will be examined for the treatment groups.

No formal inferential statistics will be applied to the vital signs data.

For each post-Baseline assessment, descriptive statistics are provided for the assessment value and the change from Baseline to the assessment with mean, median, standard deviation, minimum, and maximum at each assessment time.

6.9.3 APOE genotyping

APoE4 promotes the accumulation of β -amyloid proteins that are the cause of the characteristic plaques seen in the brains of AD subjects. The ApoE genes have consistently been associated with risk of AD dementia and will be assessed as indicated in Table 1. The genotypes will be designated as 2/2, 2/3, 3/3, 3/4, or 4/4. Data will be summarized by treatment group.

6.9.4 Routine Clinical Laboratory Measurements

Because “exacerbations” of pre-existing abnormalities in laboratory analytes are examined using clinical judgment and are reported as TEAEs, additional analysis on TEAVs is limited to subjects with values that are normal prior to dosing and abnormal after dosing. Potentially

clinically significant abnormalities in laboratory analytes are to be reported as TEAEs and summarized as clinical TEAEs.

Subjects with clinical laboratory data meeting the criteria in Section 10 of this SAP for values of potential clinical concern will be identified and summarized. Proportions of subjects with clinical laboratory values of potential clinical concern will be examined for the treatment groups.

For each post-Baseline assessment, descriptive statistics are provided for the assessment value and the change from Baseline to the assessment with mean, median, standard deviation, minimum, and maximum at each assessment time. Liver Function Tests

Liver function tests have additional analysis views for this study in accordance with current regulatory guidance. To explore the potential for drug-induced liver injury consistent with *Guidance for Industry "Drug-induced liver injury: premarketing clinical evaluation"* (CDER, CBER, July 2009), subjects will be summarized and listed who meet the following criteria:

- (1) Elevations in either AST or ALT of at least 3-times the upper limit of normal, and
- (2) An accompanying abnormal bilirubin.

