4.0 SUBJECT SELECTION**4.1 INCLUSION CRITERIA**

Subject eligibility must be reviewed and documented by an appropriately qualified member of the Principal Investigator's (PI's) study team before participants are included in the study.

1. Evidence of a personally signed and dated informed consent document indicating that the subject (or a legally authorized representative) and caregiver/informant has been informed of all pertinent aspects of the study. Participants must be able to provide consent or assent (where this is in accordance with local laws, regulations and ethics committee policy) and consent/assent must be re-evaluated during the study at regular intervals.
2. Male or female subjects aged 50-85 years (inclusive) at Screening Visit.
3. Female subjects must be of non-childbearing potential. Male subjects with female partners of child bearing potential must agree to acceptable birth control for the duration of the study and for 90 days thereafter.
4. If on pharmacological treatment for diabetes, must be on stable dose for at least 60 days prior to screening and remain stable through Baseline. There should be expectation that treatment and dose will remain stable during the study period.
5. Clinical diagnosis of probable Alzheimer's disease, consistent with the criteria from the 2011 National Institute on Aging and Alzheimer's Association workgroup [McKhann 2011], for at least 2 months prior to Screening. Evidence of progression must be documented in source documentation at the time of screening based on review of prior medical records and/or information gathered from the subject or caregiver/informant(s).
6. Mini-Mental State Exam (MMSE) score of 21-26 inclusive at Screening and 19-27 at Baseline.
7. CDR global score of 0.5 or 1 at Screening and Baseline.
8. ADAS-cog14 score of ≥ 10 at Screening and Baseline.

9. Participant must be on a stable dose of a background cholinesterase inhibitor and/or memantine (approved by relevant health authority where trial is being conducted) at least 60 days prior to Screening and remain stable through Baseline. There must be agreement not to change the treatment or dose during the study period unless the investigator judges that the dose needs to be reduced or stopped due to a safety and/or tolerability reason.
10. Hemoglobin A1c (HbA1c) 6.5% - 9.5%, inclusive, at Screening.
11. Body mass index (BMI) 19.0 – 37.0 kg/m², inclusive, at Screening Visit and Baseline Visit.

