6.2 PART 1 STUDY PERIOD

6.2.1 Part 1 / Baseline (approximately Day -7-Day 1)

- Assessment of continued consent / assent (where applicable).
- Fasting clinical laboratories:
 - Collect blood sample for plasma retention and storage.
 - Blood sample for ApoE genotyping.
 - Blood and urine sampling for safety labs including HbA1c.
 - Collect blood samples for PK and PD.
- Provide subject with a meal/snack.
- Check blood sugar, using point of care device, after an appropriate time.
 - If subject is hypoglycemic (<90mg/dL), feed the subject again and re-check blood sugar prior to neuropsychological assessments.
 - If subject is hyperglycemic (>300mg/dL), reschedule the neuropsychological assessments for a proximal day within the visit window.
- MMSE, ADAS-cog14, CDR, FAQ, Amsterdam-IADL.
- C-SSRS.

- Brief physical and neurologic examination.
- Update concomitant medications.
- Body weight.
- Assess baseline symptoms/adverse events.
- 12-lead electrocardiogram (ECG) after 5 minutes rest. Perform triplicate measures and use the average QTcF for inclusion.
- Vital signs: blood pressure (supine), pulse rate after 5 minutes rest. Perform triplicate measures and use the average blood pressure readings for inclusion.
- Review of inclusion and exclusion criteria including the results of Screening laboratories and Screening MRI scan, and confirm continued eligibility

Day 1

At the conclusion of the Baseline visit, the following procedures are performed if the subject is confirmed eligible:

- Randomize subject if eligible.
- Dispense study drug if eligible.
- Subject takes first dose of study medication in the clinic under observation and time of dosing recorded.

If the baseline assessments are performed on more than one day, up to 7 days are allowed for completion of baseline procedures prior to subject randomization and dosing. The 7-day window will begin on the day that the first baseline assessment is performed and ends on the day when the subject is randomized, and study drug is administered.

If it is necessary to extend the 7-day period for any other reason (e.g., schedule conflicts, patient/caregiver/informant illness, inclement weather) the Sponsor should be contacted for approval and the visit window may be extended up to 7 days. In this case, re-review of the inclusion/exclusion criteria and concomitant medications should occur within 7 days prior to the first dose to ensure that the patient continues

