9.8.1.3 Clinical Laboratory

Clinical Laboratory hematology and clinical chemistry variables of analysis include:

- Proportions of subjects with TEAVs (shifts from normal status to abnormal status)
- Proportions of subjects meeting DILI criteria per FDA guidance, *Guidance for Industry “Drug-induced liver injury: premarketing clinical evaluation”* (CDER, CBER, July 2009)
- Means and mean changes from Baseline to Visit
- Proportions of subjects with new (post Baseline) values (Clinical laboratory-related AEs) or changes in laboratory values of potential clinical concern

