5.2.5 Clinical laboratory assessments

Routine clinical laboratory data, including eGFR, will be summarized with descriptive statistics on assessment values and change from Baseline. Routine clinical laboratory data will also be evaluated on the basis of laboratory-defined reference ranges and clinically important values or changes, as defined in this document (Section 10). Routinely collected laboratory safety data that are not required by the protocol will be considered source data, and will not be captured for inclusion into the study database.

Definition:

- A treatment-emergent abnormal value (TEAV) is a laboratory value that is abnormal after administration of study medication that was normal prior to study medication administration.

- A TEAV of potential clinical concern is a value or change that meets criteria specified in this SAP in Section 10.

Laboratory analytes in this study include:

- Hematology
 - Hemoglobin
 - Hematocrit
 - Erythrocyte (RBC) count
 - Platelet count
 - Total leukocyte (WBC) count
 - MCV
 - Leukocyte differential (percent and total)
 - Total neutrophils
 - Eosinophils
 - Monocytes
 - Basophils
 - Lymphocytes
- Clinical chemistry
 - BUN
 - Creatinine
 - Glucose
 - HbA1c
 - Calcium
 - Sodium
 - Potassium
 - Chloride
 - Bicarbonate
 - AST
 - ALT
 - GGT
 - LDH
 - Total bilirubin
 - Alkaline phosphatase
 - Uric acid
 - Albumin
 - Total protein
 - Phosphorus

Safety variables of analysis include:

- Subjects with TEAVs
- Subjects with TEAVs of potential clinical concern (based on criteria in this SAP)
- Subjects with a TEAV in a liver function test (LFT)

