8.1 Definition of Baseline

For safety evaluations, the Baseline assessment for all measurements will be the latest available, valid measurement taken prior to the initiation study medication, except for electrocardiography (ECG) values: The Baseline assessment for ECG include a triplicate assessment with the baseline value intended to be the arithmetic mean of the values taken at the Baseline assessment that are taken in triplicate. Baseline values for efficacy outcomes will be the average of screening and baseline visits where available. For the GST, the z-scores at each visit will be calculated using the mean over all patients of the average of screening and baseline, and using the standard deviation pooled across screening and baseline.

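### Laboratory TEAVs require a normal pre-dose value, so in a population selected for raised HbA1c the HbA1c count is nearly empty; no other per-patient HbA1c rule exists, and the glucose concern rule is ambiguous

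*SAP*

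**What the plan says.** SAP 5.2.5 defines a TEAV as "a laboratory value that is abnormal after administration of study medication that was normal prior to study medication administration". SAP 6.9.4 repeats the restriction: "additional analysis on TEAVs is limited to subjects with values that are normal prior to dosing and abnormal after dosing". Protocol 9.8.1.3 uses the same normal-to-abnormal shift. The SAP gives its reason in the same sentence of 6.9.4: exacerbations "of pre-existing abnormalities in laboratory analytes are examined using clinical judgment and are reported as TEAEs".

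Protocol 4.1, criterion 10, requires "Hemoglobin A1c (HbA1c) 6.5% - 9.5%, inclusive, at Screening". HbA1c is measured again at Baseline (Protocol 6.2.1: "Blood and urine sampling for safety labs including HbA1c"), with no limit attached. Under SAP 8.1 the safety baseline "will be the latest available, valid measurement taken prior to the initiation study medication", which is normally the Baseline sample.

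HbA1c and glucose are both listed analytes in SAP 5.2.5. The concern table in SAP Section 11 has a glucose row (below 0.6 × LLN, above 1.5 × ULN) and no HbA1c row; Protocol Appendix 1 is the same. SAP 6.9.4 also gives the mean, median, SD, minimum and maximum of each value and its change from Baseline, by visit.

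**The concern.** The trial selects patients on one abnormal laboratory value and then counts treatment-emergent abnormality only from a normal start. For HbA1c the count has almost no patients at risk, so a near-zero result in both arms would say little about glycaemic control. The concern table would be the natural second line, but it omits HbA1c.

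Glycaemia matters here beyond routine safety. Complications of diabetes are a secondary objective (SAP 1.1), cognitive testing is gated on a blood glucose check (Protocol 6.0), and an HbA1c-by-treatment term is in the efficacy model (SAP 6.2). If control worsened in a subset of one arm, no planned table would show how many patients were involved.

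For glucose, a patient already abnormal at baseline cannot have a TEAV, even when moving from high to low. The concern limits could catch marked excursions, but the plan describes their relation to baseline in three different ways.

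**Working it through.** The plan states no figure on this point, so there is nothing to reproduce. The check is one of definitions, with an illustrative calculation for HbA1c.

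**1. Patients able to have an HbA1c TEAV.**

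Inputs from the documents: 43 enrolled (SAP 1.4); mean HbA1c 7.2% (SAP 1.6); Screening range 6.5–9.5% (Protocol 4.1).

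Assumptions, because the documents are silent:
- Screening HbA1c follows a truncated exponential on 6.5–9.5% with mean 7.2%. Solving 6.5 + 1/λ − 3e^(−3λ)/(1 − e^(−3λ)) = 7.2 gives λ = 1.318 and an SD of about 0.63.
- Baseline equals Screening plus normal noise with SD between 0 and 0.45 points.
- The laboratory upper limit lies between 5.7% and 6.5%.

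Expected number = 43 × P(Baseline ≤ ULN), from one million simulated values:

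| ULN | SD 0 | SD 0.15 | SD 0.30 | SD 0.45 |
|---|---|---|---|---|
| 5.7% | 0 | 0.0 | 0.02 | 0.3 |
| 6.0% | 0 | 0.0 | 0.3 | 1.4 |
| 6.4% | 0 | 1.2 | 3.6 | 5.7 |
| 6.5% | 0 | 3.1 | 5.5 | 7.5 |

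For example, at ULN 6.0% and SD 0.45, 43 × 0.0321 = 1.4. The count is near zero for the lower limits and small for the highest. It is not fixed at zero.

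**2. Glucose TEAVs.** Patients unable to have one = 43 × share abnormal at baseline. The share is not given. At 30%, 50%, 70% and 90% the result is 12.9, 21.5, 30.1 and 38.7 of 43.

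**3. Glucose concern limits.** Three descriptions stand side by side:
- SAP 5.2.5 labels the category a kind of TEAV, which may carry over the normal-baseline condition.
- Protocol 9.8.1.3 speaks of values that are new after Baseline, or of changes.
- SAP 6.9.4 counts any subject whose data meet the criteria and mentions no baseline.

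Four cases show where these differ:

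| Baseline glucose | Later glucose | 5.2.5, normal start required | Protocol 9.8.1.3, new value | 6.9.4 as worded |
|---|---|---|---|---|
| Normal | >1.5 × ULN | counted | counted | counted |
| High, ≤1.5 × ULN | >1.5 × ULN | not counted | counted | counted |
| >1.5 × ULN | still >1.5 × ULN | not counted | not counted | counted |
| High | <0.6 × LLN | not counted | counted | counted |

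Only the first case is treated alike. SAP 5.2.5 and 6.9.4 also point to Section 10 for the criteria. Section 10 is Data Displays; the criteria are in Section 11.

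**4. What remains for HbA1c.** Per-visit summary statistics give the centre, spread and extremes, but not the number of patients who worsened in each arm. The adverse-event route follows Protocol 8.1: an abnormal result is an event if it comes with symptoms, needs further testing or intervention, changes dosing or therapy, or is considered an event by the investigator or sponsor. A rise meeting none of these need not be recorded.

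**The case against.** The strongest reply is that the restriction is deliberate and explained. Worsening from an abnormal start goes to adverse events, for which Protocol 8.1 sets criteria and Protocol 8.2 designates post-dose worsening of pre-existing conditions as an event. Medically qualified staff review laboratory listings (SAP 5.2), the IDMC meets quarterly (Protocol 9.13), and change from Baseline is summarised for all patients. This stands in part: HbA1c worsening is not invisible. But the adverse-event route keeps an element of judgment, and none of these displays gives a per-arm count under a fixed rule.

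A reader might also infer more than the documents support:
- **HbA1c worsening can never be counted, or 0 of 43 by construction.** The entry limit applies at Screening only. Protocol 6.1 allows an out-of-range HbA1c to be re-tested, the safety baseline is the last pre-dose value, and no reference range is given. A few patients may start normal.
- **Glucose shifts are lost for most patients.** No baseline glucose distribution is given. If 6.9.4 is read literally, marked highs and lows are counted in everyone.
- **0 of 200 in Part 2.** This SAP covers Part 1. Protocol 9.8.1.3 carries the same shift definition, but Protocol 9.0 allows the SAP to be updated before Part 2 is unblinded.

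It is also fair to say that a single cut at 9.5% would be a poor measure: a rise from 6.6% to 9.4% would not cross it. The fix therefore adds the distribution of individual change.

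**Conclusion.** The point holds as a limited gap in safety reporting. The HbA1c TEAV count is close to uninformative, and HbA1c has no other objective per-patient rule. The expected number at risk is at most about 1.4 of 43 for assumed upper limits up to 6.0%, and up to about 7.5 of 43 at an assumed 6.5% with the largest assumed variation. These figures rest on an assumed distribution, noise and reference limit. For glucose, the mechanism is certain and the share affected is unknown. The conflict over the concern limits is a plain inconsistency that would change counts.

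The plan already counts worsening elsewhere: TEAEs include exacerbations (SAP 5.2.1), C-SSRS treatment emergence includes worsening (SAP 5.2.2), QTc has change-from-Baseline categories (SAP 6.9.5), and the liver-injury rule has a branch for raised baseline enzymes (Protocol 7.1.6.3). Laboratory TEAVs are the exception.

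**What to change.** - In SAP 5.2.5 and 6.9.4, define a treatment-emergent concern value as crossing a Section 11 limit, in a given direction, that was not already crossed at baseline, whether the baseline was normal or abnormal. In the four cases above this counts the first, second and fourth, and not the third.
- Correct the Section 10 cross-references to Section 11.
- Add a by-arm shift table of baseline against worst post-baseline HbA1c, with bands at the trial's own entry limits (<6.5%, 6.5–9.5%, >9.5%) used for tabulation only. State whether the Follow-up sample contributes to the worst value.
- Show the distribution of individual HbA1c change by arm, so that worsening within the middle band is visible.

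HbA1c is already scheduled at Baseline, Months 3 and 6, and Follow-up (Protocol 6.2), so no new data are needed. The cost is a few lines of SAP wording and one more descriptive table.
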